## 7.1.3 Definition of Study Day and Baseline

Study Day 1 is defined as the date on which a subject took the first dose of double-blind study medication, as recorded on the electronic case report form (eCRF). Other study days are defined relative to Study Day 1 with Day -1 being the day prior to Study Day 1. If the date of an event is

on or after the date of first dose then Study Day = date of event – date of first dose + 1. If the date of an event is prior to the date of first dose then Study Day = date of event – date of first dose.

The baseline value for a variable is defined as the last non-missing observation collected before first dose on Day 1 (including a screening value or unscheduled assessment, if necessary). Time of first dose is collected, so baseline value will be determined based on both date and time when the time of the measurement is also available. In the case where the last non-missing measurement (except AE and concomitant medications) and the first dose on Day 1 coincide at the same time, or the same date if time of the measurement is not collected, that measurement will be considered as baseline value

## 7.1.4 Definitions of Study Visit Windows

For each visit, a window will be defined; this window will establish a time interval around which data will be considered for the analysis of the scheduled visit pertaining to that window. The lower and upper bounds of each window are the approximate midpoints between the scheduled days for the current visit and its adjacent scheduled visits, with the exception of the Week 2 visit. The value used in analysis for by-visit summaries is the value within the specified window that is closest to the scheduled study day. If two observations are equidistant from the scheduled visit date, the observation with a later date will be used. The visit windows and applicable study day ranges are presented in Table 7.a. Cut-off days for inclusion in the window (number of days following the date of the last dose of double-blind study drug) are provided.

Table 7.a Visit Analysis Windows for Efficacy and Safety Variables

		Visit Window (Days)								
Visit	Scheduled Visit Day	Variables Scheduled at Week 2, Week 4, Week 6, Week 8	Variables Scheduled at Week 2, Week 4, Week 6	Variables Scheduled at Week 2, Week 4, Week 8	Variables Scheduled at Week 8	Variables Scheduled at Week 4, Week 8	Safety Variables Summarized by Visit			
Baseline	1	≤1	≤1	≤1	≤1	≤1	≤1			
Week 2	14	2 - 21	2 - 21	2 - 21			2 - 21			
Week 4	28	22 - 35	22 - 35	22 - 42		2 - 42	22 - 35			
Week 6	42	36 - 49	36 - Last Dose + 7				36 - 49			
Week 8	56	50 - Last Dose + 7		43 - Last Dose + 7	2 - Last Dose + 7	43 - Last Dose + 7	50 - Last Dose + Safety Cutoff			

Note: Any value collected on Day 1 but after the administration of first dose will be grouped under Week 2.

## 7.2 Significant Protocol Deviations

Significant protocol deviations collected on the eCRF will be summarized by treatment group and overall. Significant protocol deviations will also be listed.

## 7.3 Analysis Sets

The following analysis sets will be used for analysis and presentation of the study data:

**The Randomized Set** will consist of all subjects who were randomized. For subjects who were randomized more than once, only the first randomization is used.

The Safety Analysis Set will consist of all subjects who received at least one dose of double-blind study medication. Subjects will be analyzed according to the study medication they received. Subjects who were randomized more than once are excluded from the Safety Analysis Set.

The Full Analysis Set (FAS) will consist of all randomized subjects who received at least one dose of double-blind study medication. A subject in FAS will be included in the analyses of a specific variable only when there is both a baseline value and at least one value during the double-blind treatment period. Subjects will be analyzed according to the treatment group to which they were randomized. Subjects who were randomized more than once are excluded from the Full Analysis Set.

The Per Protocol Set (PPS) will consist of all subjects in the FAS, excluding those who meet following criteria:

- 1. Subjects with SBP <150 mm Hg on Day 1.
- 2. Subjects who take study drug of a different treatment from the one randomized.
- 3. Subjects who are randomized more than once.
- 4. Subjects with a significant protocol deviation impacting baseline blood pressure.
- 5. Subjects with compliance outside of the range 70%-130%.
- 6. Subjects that took a prohibited medication potentially impacting baseline or Week 8 blood pressure.

Additional criteria may be identified prior to unblinding. If so, the additional criteria will be finalized and documented prior to database lock. Subjects who are included in the FAS but excluded from the PPS will be summarized for each criterion by treatment groups and overall. These subjects will also be presented in the listings.

The Ambulatory Blood Pressure Monitoring Set (ABPM Set) will consist of the subset of FAS subjects who received an ABPM recording at baseline. Subjects who have ABPM endpoints at both baseline and at least one post dose value will be included in all ABPM related summaries and analyses. Subjects who were randomized more than once are excluded from the ABPM Set.

The FAS will be the primary data set used for efficacy analyses. Efficacy analysis based on the PPS will also be performed where appropriate. All routine safety analyses will be based on the Safety Analysis Set.

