8.1.3 Dose and Regimen

This is a phase 3, multicenter, randomized, double-blind, parallel-group, 8-week efficacy and safety study comparing TAK-491 and valsartan.

Subjects will be randomized to 1 of the following 3 therapy treatment groups as follows:

- TAK-491 40 mg QD (N=200).
- TAK-491 80 mg QD (N=200).
- Valsartan 160 mg QD (N=200).

Study medication will be packaged in a manner to maintain the blind.

CONFIDENTIAL

Placebo Run-in Period (Day-14 [Visit 2] to Day -1)

- Subjects will be dispensed one 2-week blister card and one bottle.
- Subjects will receive single-blind placebo tablets and placebo capsules.
- First dose will be given in-clinic at Day -14 (Visit 2).
- The daily oral administered dose will be two tablets from a blister card and two capsules from the bottle.

Treatment Period (Day 1 [Visit 5] through Week 8 / Early Termination [Visit 9])

- Subjects will receive blinded study medication and will be instructed to take their blinded study medication prior to their first meal of the day. Subjects will be dispensed one 2-week carton and one bottle at day 1 (Visit 5), at week 2 (Visit 6), week 4 (Visit 7), and week 6 (Visit 8).
- First dose will be given in-clinic at Day 1 (Visit 5).
- The daily oral administered dose will be two tablets from a blister card and two capsules from the bottle

Table 8.a describes the dose and tablet/capsule count that will be provided to each group.

Table 8.a Sponsor-Supplied Drug

Treatment Group		Treatment Description		
	Dose	Active	Placebo	
	Run-in QD	Zero active tablets/capsules	One placebo for 40 mg TAK-491 tablet, one placebo for 80 mg TAK-491 tablet, two placebo for 80 mg valsartan capsules	
A	40 mg TAK-491 QD	One 40 mg TAK-491 tablet	One placebo for 80 mg TAK-491 tablet, two placebo for 80 mg valsartan capsules	
В	80 mg TAK-491 QD	One 80 mg TAK-491 tablet	One placebo for 40 mg TAK-491 tablet, two placebo for 80 mg valsartan capsules	
C	160 mg valsartan QD	Two 80 mg valsartan O/E capsules	One placebo for 40 mg TAK-491 tablet, one placebo for 80 mg TAK-491 tablet	

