9.2 Monitoring Subject Treatment Compliance

Subjects will be required to bring study medication containers to each clinic visit, regardless of whether the study medication container is empty.

If a subject is persistently noncompliant with the study medication (<70% or >130% of the allocated medication for the period since the last visit), it may be appropriate to withdraw the subject from the study. All subjects should be reinstructed about the dosing requirement during study contacts. The authorized study personnel conducting the re-education must document the process in the subject source records.

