## 7.8 Study Drug Exposure and Compliance

The duration of exposure to double-blind study medication is defined as date of last dose of double-blind study drug - date of first dose double-blind study drug + 1. The date of last double-blind dose will be obtained from the eCRF. In the event that the date of last dose is missing, the last dose date will be estimated as the later date between the last drug dispense date plus the number of days in the dosing interval (dispense date + next visit day – last visit day + 1) and the last study visit day for analysis and summary purposes.

The duration of exposure to double-blind treatment will be summarized by treatment group as a continuous variable and tabulated using following categories: 1 to 7 days, 8 to 14 days, 15 to 21 days, 22 to 28 days, 29 to 35 days, 36 to 42 days, 43 to 49 days, 50 to 56 days, 57 to 63 days and 64 days or more.

Subjects are to take 2 tablets for TAK-491 (40 mg/80 mg) and matching placebo or 2 capsules for valsartan and matching placebo each day. Overall percent study drug compliance for the double-blind treatment period will be calculated as:  $100 \times [\text{(number of tablets dispensed - number of tablets returned)}/(\text{expected number of tablets to be taken)}], where the expected number of tablets to be taken = [4*(date of last dose of medication - date of first dose of medication + 1)]. Compliance will be presented to 1 decimal place in the derived dataset.$ 

Overall double-blind study drug compliance will be summarized using descriptive statistics and by the number of subjects in each of the following compliance categories: <70%, 70 to 130%, >130%. A missing category will also be included, if applicable.

The summary of study drug exposure and compliance will be based on the Safety Analysis Set. No inferential statistics will be presented.

The above tables will also be provided for the ABPM subgroup. A compliance for ABPM procedure will be provided. The number and percentage of subjects with qualified ABPM recordings will be summarized by treatment group and overall at baseline and Week 8.

All study drug administration (single-blind placebo and double-blind study drug) and accountability data will be listed by site and subject number.

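### The Per Protocol limit of 70%-130% is applied to one compliance figure pooled over tablets and capsules, so under selective skipping it allows active intake as low as 0% on TAK-491 but 40% on valsartan

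*SAP*

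**What the plan says.** SAP 7.3, criterion 5, takes out of the PPS "Subjects with compliance outside of the range 70%-130" per cent. It does not say how compliance is computed and does not refer to another section.

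SAP 7.8 holds the only definition for the double-blind period. "Overall percent study drug compliance for the double-blind treatment period will be calculated as" 100 times the ratio of "number of tablets dispensed - number of tablets returned" to the expected number, "4*(date of last dose of medication - date of first dose of medication + 1"), that is, 4 units per day of treatment. The compliance table in SAP 7.8 uses the same cut-points, 70% and 130%.

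The double-dummy is set out in Protocol 8.1.3: "The daily oral administered dose will be two tablets from a blister card and two capsules from the bottle". Table 8.a there gives the content by arm:

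- TAK-491 40 mg: one active tablet; the placebo units are "one placebo for 80 mg TAK-491 tablet, two placebo for 80 mg valsartan capsules".
- TAK-491 80 mg: one active tablet; the other tablet and both capsules are placebo.
- Valsartan: "Two 80 mg valsartan O/E capsules"; both tablets are placebo.

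SAP 7.9.1 uses the PPS for sensitivity analyses of the primary endpoint: the primary model repeated, multiple imputation, and observed cases. The Full Analysis Set (FAS) is the primary set (SAP 7.3).

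**The concern.** A compliance criterion in a per-protocol set is meant to ensure that the retained subjects took enough of their assigned drug. A figure pooled over a double-dummy measures units swallowed and cannot tell a missed placebo from a missed active dose. Because the active share of the daily units differs by arm, the same 70% does not guarantee the same minimum active intake.

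The first two steps of the sequential test are noninferiority tests with a 1.5 mm Hg margin, and the PPS is one of the named checks on their robustness. A PPS that can retain a subject with no active exposure is a weaker check than its name suggests. The compliance table has the same limitation.

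**Working it through.** **Reproducing the factor 4.** 2 tablets + 2 capsules = 4 units a day, so full adherence gives 4/4 = 100% whatever the duration. SAP 7.8 speaks only of tablets in the numerator and describes the daily intake as tablets or capsules. Counting tablets alone over 4 per day would give a fully adherent subject 2/4 = 50%, and everyone would fail the 70% limit. The pooled count is therefore the only workable reading. That criterion 5 uses this formula is an inference, supported by the identical cut-points and the absence of any other definition.

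**Score and active intake by skipping pattern** (all other units taken):

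| Pattern | Score, any arm | PPS | Active intake, TAK-491 | Active intake, valsartan |
|---|---|---|---|---|
| One tablet type never taken | 3/4 = 75% | kept | 0% or 100%, depending on the tablet | 100% |
| One capsule a day instead of two | 3/4 = 75% | kept | 100% | 50% |
| Both tablets never taken | 2/4 = 50% | removed | 0% | 100% |
| Both capsules never taken | 2/4 = 50% | removed | 100% | 0% |
| 30% of days missed entirely | 70% | kept | 70% | 70% |

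The score column is the same in all arms; only the active drug behind it differs.

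**Lowest active intake x that still scores 70%, with all placebo taken.**

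- TAK-491: (3 + x)/4 is already 75% at x = 0, so the floor is 0%.
- Valsartan: (2 + 2x)/4 = 0.70 gives x = 0.40.

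**Upper limit.** Doubling the active units daily scores 5/4 = 125% on TAK-491 (kept) and 6/4 = 150% on valsartan (removed).

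**Possible effect on the PPS estimate.** The documents give no rate of selective skipping, so these are illustrations. Suppose a share p of a TAK-491 arm's PPS takes no active tablet and loses an effect of 8.6 mm Hg (the valsartan figure in SAP 7.9.1, as a proxy) to 14.6 mm Hg (8.6 + the planned 6).

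- p = 1%: 0.01 × 8.6 = 0.09 to 0.01 × 14.6 = 0.15 mm Hg against TAK-491.
- p = 5%: 0.05 × 8.6 = 0.43 to 0.05 × 14.6 = 0.73 mm Hg, which is 29% to 49% of the 1.5 mm Hg margin.

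The opposite shift is also possible. If 5% of the valsartan PPS takes half the capsules and effect is proportional to dose, the difference moves 0.05 × 4.3 = 0.22 mm Hg in favour of TAK-491.

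**The same cases under a container-level rule.** The TAK-491 subject without the active tablet scores 1/2 = 50% on tablets; the valsartan subject without capsules scores 0% on capsules. Both are removed. The floors become (1 + x)/2 = 0.70, so x = 0.40 on TAK-491, and 70% on valsartan. By tablet strength the TAK-491 floor is also 70%.

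**The case against.** The strongest objection is that the rule is even-handed about behaviour. A reader might set the TAK-491 subject who scores 75% without active drug beside the valsartan subject who scores 50% without it, and infer that the PPS filters the arms differently by construction. Those two subjects did different things: one left a single tablet type, the other left the whole bottle. Each pattern scores the same in every arm, and missed whole days cost every arm the same share of active drug. That stands; the inequality is in what the score implies about active intake, and only when skipping is selective.

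Zero active intake is also a boundary case. It needs the subject to leave one tablet type on the card throughout while taking the other tablet and both capsules. Medication is collected and compliance assessed at Visits 6 to 9, with in-clinic dosing at each (Protocol 9.3.6 and Appendix A). If the choice of tablet is unrelated to its hidden content, 5% of subjects without active drug would require about 10% who consistently skip one tablet type. No document figure supports such a rate.

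The size needs context too. On the planning figures (SD 17, true difference -6, 200 × 0.90 = 180 per arm), the standard error is 17 × √(2/180) = 1.79 and the expected upper confidence limit is -6 + 1.96 × 1.79 = -2.5. Adding 0.73 gives about -1.8, still well below 1.5. A shift against TAK-491 is conservative for noninferiority.

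Finally, SAP 7.3 lets PPS criteria be added before unblinding, Protocol 13.1 provides a blinded review of evaluability, and accountability data are listed, so a selective skipper could be found. These make a remedy possible, but none of the listed criteria supplies one.

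**Conclusion.** The point holds as a limited one. The pooled figure can keep a subject with no active exposure in the PPS, and the 70% limit guarantees at least 0% active intake on TAK-491 against 40% on valsartan. These floors follow directly from Table 8.a and the factor 4. They assume that criterion 5 uses the SAP 7.8 formula and that all placebo units are taken.

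The documents do not support three stronger readings. The primary conclusion is not at risk, because the FAS carries the sequential test and the PPS is a sensitivity set. A bias of 29% to 49% of the margin is not shown, because it rests on an assumed 5% rate and a proxy effect. Nor is it shown that under-dosing goes unnoticed during the trial: Protocol 9.2 states its limit as "<70% or >130% of the allocated medication for the period since the last visit" and does not specify a pooled figure, and the run-in compliance criterion concerns an all-placebo period. No change to Protocol 9.2 or exclusion criterion 2 is proposed.

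This is a cheap improvement to the PPS definition and the compliance table.

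**What to change.** In SAP 7.8, compute double-blind compliance separately for tablets (2 per day) and capsules (2 per day), and by tablet strength if returned counts are recorded that way. In SAP 7.3, reword criterion 5 to exclude a subject when any component is outside 70%-130%, applied before unblinding. Every subject receives the same tablets-and-capsules layout, so this needs no treatment code.

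By container, the floors rise from 0% and 40% to 40% and 70%, which narrows the gap from 40 to 30 points without closing it. Equal floors of 70% need counts by strength. Each card holds twenty of each tablet type (Protocol 8.1.1.1), but the documents do not say that returns are recorded by type, so this should be confirmed first.

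For the container version the cost is SAP wording and programming, since cards and bottles are separate items. The downside is some additional PPS exclusions, including subjects who missed only placebo. For example, a TAK-491 subject with all tablets and 60% of the capsules scores (2 + 1.2)/4 = 80% and is kept now, but would be removed at 60% on capsules. Summarising exclusions by component would show how many there are.

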## 7.4 Disposition of Subjects

Disposition of all screened subjects will be tabulated (count and percent); there will be no inferential analysis of subject disposition data.

Disposition of non-randomized subjects will be tabulated according to screen failure and run-in failure, including primary reason for screen or run-in failure (pretreatment event/adverse event, major protocol deviation, lost to follow-up, voluntary withdrawal, study termination, did not meet entrance criteria or other) as entered on the eCRF.

Disposition of all randomized subjects will be tabulated by randomized treatment. For subjects who were randomized more than once, only the first randomization is used in the summary. The categories will include:

- Randomized subjects.
- Subjects who were randomized but not treated with double-blind study drug.
- Subjects who completed double-blind study drug.
- Subjects who prematurely (permanently) discontinued double-blind study drug.
- Subjects unblinded by the investigator (inadvertently or for safety reasons).

The primary reason for discontinuation of study drug and/or study visits (pretreatment event/adverse event, major protocol deviation, lost to follow-up, voluntary withdrawal, study termination, pregnancy, lack of efficacy and other), as entered on the eCRF, will be tabulated for all randomized subjects.

The above summaries will also be performed for ABPM subgroup subjects.

Double-blind treatment group, date of first double-blind dose, date of last double-blind dose, duration of treatment (study day of last dose) and the reason for premature discontinuation of study drug/study visit will be listed for each randomized subject in the listings. Subjects in ABPM subgroup will be flagged. A listing of inclusion/exclusion criteria responses by subject will also be provided.

## 7.5 Demographic and Baseline Efficacy Characteristics

## 7.5.1 Demographic and Baseline Characteristics

Demographic and baseline characteristics, including age (years) at the date of informed consent, gender, race, height (cm), weight (kg), body mass index (BMI) (kg/m²), smoking classification, female reproductive status, estimated glomerular filtration rate (eGFR) (mL/min/1.73m²) and baseline HbA1c (%) will be summarized for each treatment group and overall using the Safety Analysis Set. Demographic and baseline characteristics for the ABPM subgroup will also be summarized.

Age is computed as the difference in years between date of birth and informed consent date; one decimal will be kept for age in derived data. Age will be summarized as a continuous variable and will also be tabulated using the following categories: <45 years, 45 to 64 years, <65 years, ≥65 years and ≥75 years.

Race will be recorded on the eCRF as American Indian or Alaska Native, Asian, Black or African American, Native Hawaiian or Other Pacific Islander and White. Subjects who identify themselves as more than one race on the eCRF will be classified as Multiracial for tabulation, and will be included only in the Multiracial category.

Baseline BMI is derived as: BMI  $(kg/m^2)$  = (baseline weight in kg)/((height in cm)/100); one decimal will be kept for baseline BMI in derived data. BMI will be summarized as a continuous variable and will also be tabulated using the following categories:  $<27 \text{ kg/m}^2$  and  $\ge 27 \text{ kg/m}^2$ .

Baseline eGFR will be summarized as a continuous variable and will also be tabulated using the following categories:  $<30 \text{ mL/min/1.73m}^2$ ,  $30 \text{ to } <60 \text{ mL/min/1.73m}^2$ ,  $60 \text{ to } <90 \text{ mL/min/1.73m}^2$  and  $\ge 90 \text{ mL/min/1.73m}^2$ .

There will be no inferential analysis of these demographic and baseline characteristics.

All individual demographic and baseline characteristics will be listed by treatment, study centre and subject number. The demographic data listing will include subject identifier, treatment, date of informed consent, date of birth, age at date of informed consent, gender, race, height, baseline weight and baseline BMI. Smoking classification, female reproductive status, baseline HbA1c level, baseline clinic measures of SBP and DBP and baseline eGFR will also be presented in a data listing.

## 7.5.2 Baseline Efficacy Parameters

Baseline values of continuous efficacy endpoints will be summarized and analyzed using an analysis of variance (ANOVA) with treatment as a fixed factor. These endpoints include calculated mean sitting SBP and DBP. For ABPM subgroup subjects, the endpoints include all ABPM parameters.

Baseline calculated mean sitting SBP and DBP will be summarized as continuous variables. Further, baseline calculated mean sitting SBP will be tabulated using the following categories: 140 to <160 mm Hg, 160 to <180 mm Hg and ≥180 mm Hg. A separate tabulation will be completed for the following categories: <median baseline calculated mean sitting SBP and ≥median baseline calculated mean sitting SBP. Baseline calculated mean sitting DBP will be tabulated using the following categories: <90 mm Hg and ≥90 mm Hg.

The baseline efficacy parameters will also be listed.

